6.2. Randomization

Subjects will be screened and approximately 400 eligible subjects will be randomized by the IRT system: 200 subjects will be randomized to inclisiran sodium 300 mg and 200 subjects randomized to placebo. Due to faster than expected enrollment, actual enrollment was 482 subjects. Treatment allocation will be stratified by country and by current use of statins or other lipid-modifying therapies. Each subject will receive four subcutaneous (SC) injections of blinded inclisiran or placebo on Day 1, Day 90, Day 270, and Day 450.

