The primary endpoints will use a reflexive LDL-C approach: either calculated LDL-C (based on the Friedewald formula) will be used, or if the calculated LDL-C is less than 40 mg/dL or triglycerides are greater than 400 mg/dL, or calculated LDL-C is missing, directly measured (using ultracentrifugation) LDL-C will be used if it is available.

Percentage change in LDL-C from baseline to Day 510

Missing values will be imputed for LDL-C after a reflexive approach using the multiple imputation (100 total imputed datasets) washout model specified in Appendix 2. The percentage change in LDL-C at each visit will be calculated after the missing data imputation has been performed.

The primary analysis will be conducted on the ITT population and based on an ANCOVA model on the percentage change in LDL-C from baseline to Day 510 on each multiply imputed dataset

(100 total). The model will include the fixed effect of treatment group and baseline LDL-C as a covariate.

Treatment effects from these 100 ANCOVA analyses will then be combined using Rubin's Method via the SAS PROC MIANALYZE procedure. The difference in the least squares means between treatment groups and corresponding two-sided 95% confidence interval will be provided for hypothesis testing.

See Appendix 2 for more details on this analysis.

Time adjusted percentage change in LDL-C from baseline after Day 90 and up to Day 540.

A control-based pattern-mixture model (PMM), following the methods described in Ratitch and O'Kelly (2011), will be utilized to explore the possibility of data missing not at random (MNAR) for subjects who discontinued the study. For subjects who discontinued the study without any further follow-up data, their missing values after study discontinuation will be imputed under the assumption that their outcome would be similar to those in the placebo group with similar background characteristics. For subjects who did not discontinue the study, their intermittent missing values will be imputed based on the MAR assumption. Multiple imputations will be used to account for uncertainty in the imputation process and results from the imputed datasets will be combined using Rubin's method [Rubin, 1987]. See Appendix 3 for more details on this analysis.

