The primary analysis will be conducted on the ITT population and based on a mixed-effects model for repeated measurements (MMRM) on the percentage change in LDL-C from baseline over all visits on each multiply imputed dataset (100 total). The model will include fixed effects for treatment, visit, baseline value, and the interaction between treatment and visit. The Restricted Maximum Likelihood (REML) estimation approach will be used with the covariance structure set as "Unstructured" (refer to Appendix 1 for further details on the MMRM).

The time adjusted percentage change in LDL-C from baseline after Day 90 and up to Day 540 will be calculated from the MMRM. Linear combinations of the estimated means after Day 90 and up to Day 540 will be used to compare treatment effects. Note that Day 90 will be excluded from the MMRM.

Treatment effects from these 100 MMRM analyses will then be combined using Rubin's Method via the SAS PROC MIANALYZE procedure. The difference in the least squares means between treatment groups and corresponding two-sided 95% confidence interval will be provided for hypothesis testing.

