6.4.6.1.1. Sensitivity Analysis for Primary Efficacy Endpoints

In order to support the robustness of the conclusions drawn from the co-primary efficacy analyses, we will perform the following sensitivity analyses for the co-primary efficacy endpoints.

Percentage change in LDL-C from baseline to Day 510

• A control-based pattern-mixture model (PMM), using the same imputed datasets and MMRM model that was used for the second co-primary efficacy endpoint primary analysis will be used to compare treatments at Day 510. Multiple imputations will be

used to account for uncertainty in the imputation process and results from the imputed datasets will be combined using Rubin's method. (Refer to Appendix 3 for details)

- A mixed model for repeated measurements (MMRM) analysis without multiple imputation, that assumes missing data are missing at random (MAR), will be performed. The model will include fixed effects for treatment, visit, baseline value, and the interaction between treatment and visit. The Restricted Maximum Likelihood (REML) estimation approach will be used with the covariance structure set as "Unstructured". A linear contrast at Day 510 will be used to compare treatment groups. This will be the same model that is used as a sensitivity analysis for the second co-primary endpoint.
- The impact of country and current use of statins or other lipid-modifying therapies will be assessed by including country (possibly pooled into a region), the treatment-by-country interaction, and current use of statins or other lipid-modifying therapies (yes or no) as fixed effects into the primary efficacy analysis ANCOVA (using multiple imputation washout model data).
- An ANCOVA model without multiple imputation will be performed using the mITT population. The model will include the fixed effect of treatment group and baseline LDL-C as a covariate.
- A tipping point analysis will be performed to search for the tipping point that reverses the study conclusion. In the tipping point analysis, we will independently vary the deltas in the treatment groups (inclisiran group progressively worse while the placebo group is not impacted and inclisiran group progressively worse while the placebo group progressively improves) until the hypothesis test on the co-primary efficacy endpoint becomes statistically insignificant.

Time adjusted percentage change in LDL-C from baseline after Day 90 and up to Day 540.

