- A mixed model for repeated measurements (MMRM) analysis without multiple imputation, that assumes missing data are MAR, will be performed. The model will include fixed effects for treatment, visit, baseline value, and the interaction between treatment and visit. The Restricted Maximum Likelihood (REML) estimation approach will be used with the covariance structure set as "Unstructured". A linear combination of the estimated means after Day 90 and up to Day 540 will be used to compare treatment groups. This will be the same model that is used as a sensitivity analysis for the first coprimary endpoint.
- The impact of country and current use of statins or other lipid-modifying therapies will be assessed by including country (possibly pooled into a region), the treatment-by-country interaction, and current use of statins or other lipid-modifying therapies (yes or no) as fixed effects into the primary efficacy analysis MMRM (using multiple imputation control-based PMM data).
- The time adjusted percentage change will also be calculated by taking the arithmetic mean of calculated percent change in LDL-C from baseline at each visit after Day 90 through Day 540. This analysis will be based on the control-based PMM imputed datasets (100 multiple imputation datasets). The two sample t-test will be performed to test the

treatment difference between inclisiran and placebo. Results will be combined and summarized using Rubin's method.

 A tipping point analysis will be performed to search for the tipping point that reverses the study conclusion. In the tipping point analysis, we will independently vary the deltas in the treatment groups (inclisiran group progressively worse while the placebo group is not impacted and inclisiran group progressively worse while the placebo group progressively improves) until the hypothesis test on the co-primary efficacy endpoint becomes statistically insignificant.

Other sensitivity analysis may be performed.

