8. CHANGES TO ANALYSES SPECIFIED IN THE PROTOCOL

The following items were changed between the final version of the protocol and the final SAP.

- Primary efficacy endpoint analyses were modified per FDA feedback.
- Due to the distribution of the data, current use of statins or other lipid-modifying therapies at baseline (yes or no) was removed from the primary analyses and included as factors in the models of the sensitivity analyses.
- Imputation methods were modified per FDA feedback.
- Subgroup analyses were added for select variables.
- A secondary efficacy endpoint was renamed from mean maximum percent change to maximum percent change.
- The exploratory endpoint, proportion of subjects in each group with any LDL-C reduction from baseline at any visit (responders), was added
- Identification of PCS/CS laboratory values were modified.

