2.4. Statin/LMT Use at Baseline

The small number of subjects who were not currently using statins or other lipid-modifying therapies (LMT) at baseline caused convergence issues with the imputation models. As such, the statin/LMT use at baseline effect was removed from the multiple imputation washout model and Control Based - Pattern Mixture Model imputation steps. Note that the statin/LMT use at baseline effects were already removed from the analysis models.

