- 5. The imputed data from Step #3 will be combined with the imputed data from Step #4 to create 100 fully imputed datasets.
- 6. A total of 100 fully imputed datasets will be created (M=100). Since multiple imputation is a stochastic method, slight differences in output can be expected for different initial states of the random number generator. The seed numbers will be identified in the SAS programs to allow for reproducibility.
- 7. After the missing data imputation is completed using the above steps, absolute change/percentage change values will be calculated in each of the imputed datasets at each visit.
- 8. These 100 datasets will be analyzed using ANCOVA models with fixed effect of treatment group and baseline LDL-C as a covariate for the percent change of LDL-C from baseline to Day 510 primary efficacy endpoint.
- 9. Treatment effects (difference in LS means between treatments) from these 100 analyses will then be combined using Rubin's Method via SAS PROC MIANALYZE procedure for each endpoint.

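### Randomisation is stratified by country, but neither co-primary model includes country and no planned analysis adjusts for it as a main effect alone, so the reported intervals may be slightly too wide

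*SAP*

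**What the plan says.** SAP 6.2 (Randomization): "Treatment allocation will be stratified by country and by current use of statins or other lipid-modifying therapies".

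SAP 6.4.6.1 gives the two co-primary models.

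- Percentage change at Day 510, ANCOVA: "The model will include the fixed effect of treatment group and baseline LDL-C as a covariate". The addendum (section 2.5) keeps this: "These 100 datasets will be analyzed using ANCOVA models with fixed effect of treatment group and baseline LDL-C as a covariate".
- Time-adjusted percentage change, MMRM: "The model will include fixed effects for treatment, visit, baseline value, and the interaction between treatment and visit".

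The key secondary endpoints (SAP 6.4.6.2 and Appendix 1) use the same MMRM terms, again without country.

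The SAP explains why the other stratification factor was dropped. Section 8 says that "current use of statins or other lipid-modifying therapies at baseline (yes or no) was removed from the primary analyses", because of the distribution of the data. Addendum 2.4 reports convergence problems, so that "the statin/LMT use at baseline effect was removed from the multiple imputation washout model" and from the control-based pattern-mixture imputation. Neither place mentions country. The protocol's model (10.4.3.1) contained therapy use but not country.

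Country appears in one sensitivity analysis for each co-primary endpoint (SAP 6.4.6.1.1). For Day 510, the ANCOVA is extended by "including country (possibly pooled into a region), the treatment-by-country interaction, and current use of statins or other lipid-modifying therapies". For the time-adjusted endpoint the same set is added "as fixed effects into the primary efficacy analysis MMRM". Table 3 (SAP 6.4.7) also lists region as a subgroup: North America, Europe and South Africa.

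**The concern.** Stratifying by country balances the arms within each country, so differences between countries largely drop out of the treatment comparison. The precision is gained at allocation. A model without country leaves those differences in its residual variance and reports a standard error that is too large. SAP 6.4.6.1 makes the 95% confidence interval the basis for hypothesis testing, so its accuracy matters.

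The sensitivity models do not close the gap. With a treatment-by-country interaction, the overall treatment effect depends on how the country effects are weighted, and the SAP does not say how. The same models bring back the therapy-use factor that was too sparse for the imputation models, and pooling of countries is left open with no rule. For the key secondary endpoints, the only stated sensitivity analysis is the MMRM without imputation, which has no country term.

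At stake is the accuracy of the reported intervals, not the superiority claim.

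**Working it through.** **Inputs from the documents.** Difference 30 and SD 20 (stated in mg/dL), 400 randomised 1:1, 5% dropout, 380 evaluable, one-sided alpha 0.025 and actual enrolment 482 (SAP 6.1 and 6.2); two-sided alpha 0.05 (SAP 6.4.6.1).

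**Assumptions.** SD 20 is read as percentage points of LDL-C change. The 482 subjects are split 241/241. R² is the share of variance, after baseline LDL-C, that country explains. The documents do not give it, so it is varied from 0 to 0.10.

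**The plan's own figure.** 400 × 0.95 = 380, or 190 per arm. The standard error is 20 × √(2/190) = 2.05, and 30/2.05 = 14.6. Power therefore exceeds 99.99%, consistent with the stated figure of more than 90%.

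**Effect of leaving country out.** With allocation balanced within country:

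- reported SE = SD × √(2/n) = 20 × √(2/241) = 1.822
- true SE = reported SE × √(1 − R²)
- overstatement = 1/√(1 − R²) − 1
- reported half-width = 1.96 × 1.822 = 3.57
- correct half-width = 3.57 × √(1 − R²)
- two-sided size = 2 × [1 − Φ(1.96/√(1 − R²))]

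| Assumed R² | SE too large by | Reported half-width | Correct half-width | Actual size | Actual coverage |
|---|---|---|---|---|---|
| 0 | 0% | 3.57 | 3.57 | 0.050 | 95.0% |
| 0.02 | 1.0% | 3.57 | 3.54 | 0.048 | 95.2% |
| 0.05 | 2.6% | 3.57 | 3.48 | 0.044 | 95.6% |
| 0.10 | 5.4% | 3.57 | 3.39 | 0.039 | 96.1% |

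**Simulation check.** Assumed: 482 subjects, 8 countries of 20 to 120 subjects grouped into 3 regions, blocks of 4 within country, 12,000 runs per R², ANCOVA on complete data. Monte Carlo error of the size is about 0.002.

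| R² | True SD of estimate | Mean SE, no country | Mean SE, country | Mean SE, 3 regions | Size (none / country / regions) |
|---|---|---|---|---|---|
| 0.10 | 1.73 | 1.823 | 1.729 | 1.796 | 0.039 / 0.049 / 0.042 |
| 0.05 | 1.776 | 1.823 | 1.777 | 1.810 | 0.043 / 0.050 / 0.045 |
| 0 | – | 1.823 | 1.823 | 1.823 | 0.050 in all three |

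Pooling every country into 3 regions leaves most of the overstatement: about 3.9% instead of 5.4% at R² = 0.10, and about 1.9% instead of 2.6% at R² = 0.05. The correction is therefore smaller than the formula gives if countries are pooled.

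A second simulation (3, 8 or 12 assumed countries, 4,000 runs each) gave mean half-widths of about 3.58 without country, and 3.55, 3.49 and 3.40 with it at R² = 0.02, 0.05 and 0.10. At R² = 0.10 the size without country was 0.031 to 0.040.

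**Why the interaction model is no substitute.** Take assumed country sizes of 20, 30, 40, 50, 60, 72, 90 and 120 (total 482), with balanced arms. If country effects are weighted equally, the variance relative to the simple comparison is (482/64) × Σ(1/nₖ) = 7.53 × 0.1783 = 1.34. The standard error is then √1.34 = 1.16 times as large, before any gain from explained variance. Such an interval cannot serve as a check on the primary one.

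**The case against.** The strongest reply is that nothing depends on this. The planned difference is 30/1.822 = 16.5 standard errors. Even at R² = 0.10 the half-width moves by only 0.18 points, and the error is conservative. That stands: the matter is interval accuracy and nothing more.

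Second, the size is assumed. The documents give no R² for country, no country sizes and no block size, and R² = 0 fits them as well as 0.10 does. That also stands, which is why the result is a range that includes zero. At zero, adding country costs only a few degrees of freedom.

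Third, the figures are for a complete-data ANCOVA. The time-averaged MMRM and the pooling over imputations were not computed. The same reasoning gives the direction for them, but the exact percentages should not be carried over.

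Fourth, country is already examined in the two sensitivity models and the region subgroups, and an interaction model averaged over countries is itself a stratified estimate. This holds only in part. The weights are unstated, the sparse factor is included, and separate regional estimates do not make one adjusted estimate.

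Fifth, SAP section 8 lists changes from the protocol, and country was never in the protocol's model, so its silence there is not a lapse. That is fair, but it still leaves no reason in either document for omitting a stratification factor.

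Finally, the study was unblinded before the addendum, and one sparse binary factor had already caused convergence trouble in imputation. Both points are valid and limit the remedy.

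**Conclusion.** The concern holds. Country is a stratification factor, it is missing from both co-primary models and from the key secondary models, and no specified analysis adjusts for it as a main effect alone. The reported standard errors may be too large by 0 to 5.4% for an assumed R² of 0 to 0.10, with true coverage of 95.0 to 96.1% for nominal 95% intervals. These figures rest on the assumed R², SD 20 read as percentage points, a 241/241 split and complete data. The effect is small and conservative. Type I error is not inflated and the superiority conclusions are not at risk. The absences are certain from the text; the size is not, because R² is unknown.

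**What to change.** The addendum's introduction says that the SAP was final, the database locked and the study unblinded. The primary models should therefore stay as they are. Report, as a labelled supplementary analysis for each co-primary and key secondary endpoint, the same model with a country main effect and no interaction. Keep countries separate where numbers allow, and pool small ones into the Table 3 regions by a rule written down before the analysis is run. Add country to the imputation models where it can be estimated. Where it cannot, say so. Leave therapy use out, for the reason the SAP gives. State the weights used for the overall effect in the existing treatment-by-country sensitivity models. The cost is one supplementary table per endpoint.

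In a plan not yet unblinded, the country main effect would go directly into the co-primary ANCOVA and MMRM and the key secondary MMRMs, with treatment-by-country kept for sensitivity. That costs a few degrees of freedom out of about 480 and a little programming.

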APPENDIX 1. DETAILS OF MMRM USED FOR EFFICACY ANALYSES

A number of efficacy analyses will utilize a mixed-effects model for repeated measures (MMRM). This includes the co-primary efficacy endpoints (in the case of the first co-primary efficacy endpoint, it will be used as a sensitivity analysis), the key secondary efficacy endpoints, and other secondary efficacy endpoints.

The models will generally include fixed effects for treatment, visit, baseline value, and the interaction between treatment and visit. The current use of statins or other lipid-modifying therapies will also be included as a fixed effect for some sensitivity analyses. The visits will include Days 90, 150, 270, 330, 450, and 510, with Day 510 as the primary time-point. Linear combinations of the estimated means will be created for the various hypothesis tests. Note that for time adjusted percentage change analyses (second co-primary efficacy endpoint) Day 90 will be excluded from the models.

The Restricted Maximum Likelihood (REML) estimation approach will be used with the covariance structure set as "Unstructured." The least squares means will be calculated for each treatment at each visit.

The analysis will be carried out using the SAS PROC MIXED procedure.

Sample SAS statements follow:

```
ods output LSmeans=estimates;
ods output Diffs=lsdiffs;
Proc Mixed Data=ldl_data;
   Class treatment visit_day subject_id;
   Model percent_change = treatment|visit_day base_value/DDFM=KR;
repeated visit_day/type=UN subject=subject_id;
LSMeans treatment*visit_day/cl pdiff=control('0' '510');
run;

(where ('0' '510') is the value of the placebo ['0'] at day 510 ['510'] in interaction term treatment*visit_day)
```

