APPENDIX 3. CONTROL-BASED PATTERN MIXTURE MODEL

A control-based Pattern-Mixture Model (PMM) will be used to explore the possibility of data missing not at random (MNAR) for subjects who discontinued the study. For subjects who discontinued the study without any further follow-up data, their missing values after study discontinuation will be imputed under the assumption that their outcome would be the similar to those in the placebo group with similar background characteristics. For subjects who did not discontinue the study, their intermittent missing values will be imputed based on the MAR assumption. Multiple imputation will be used to account for uncertainty in the imputation process and results from the imputed datasets will be combined using Rubin's method. Further details are provided below.

Windowing will be performed first (see Section 6.3.3) and any missing data will be imputed using the following steps.

The covariates and baseline characteristics which can be predictive of the response will be included in a multiple imputation procedure (SAS PROC MI) and will include the following:

- Baseline value of efficacy measurement (continuous)
- Observed value of efficacy measurement at Day 90 (continuous)
- Observed value of efficacy measurement at Day 150 (continuous)
- Observed value of efficacy measurement at Day 270 (continuous)
- Observed value of efficacy measurement at Day 330 (continuous)
- Observed value of efficacy measurement at Day 450 (continuous)
- Observed value of efficacy measurement at Day 510 (continuous)
- Observed value of efficacy measurement at Day 540 (continuous)
- Current use of statins or other lipid-modifying therapies (categorical)
- 1. Intermittent missing data will be imputed using MCMC methods, assuming MAR, within each treatment group. SAS PROC MI will be utilized for this step using the MCMC impute=monotone option. A total of 100 datasets will be created. These datasets will be utilized in Step #2.

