- 2. The remaining missing values with a monotone missing data pattern will be imputed in this step. Control-based PMM imputation will be performed. With this imputation model, the missing efficacy measurements in the inclisiran group will not be constructed from the observed data in the inclisiran group but rather from the observed data in the placebo group. We will also use this model to impute missing efficacy measurements in the placebo group. The MNAR statement in SAS PROC MI will be used to impute missing values under the aforementioned assumptions. This will be performed for the 100 datasets. After this step, the 100 datasets will be fully imputed.
- 3. A total of 100 fully imputed datasets will be created (M=100). Since multiple imputation is a stochastic method, slight differences in output can be expected for different initial states of the random number generator. The seed numbers will be identified in the SAS programs to allow for reproducibility.

- 4. After the missing data imputation is completed using the above steps, absolute change/percentage change values will be calculated in each of the imputed datasets at each visit.
- 5. These 100 datasets will be analyzed using the MMRM described in Appendix 1 for the coprimary efficacy endpoints and key secondary efficacy endpoints.
- 6. Treatment effects (difference in LS means between treatments) from these 100 analyses will then be combined using Rubin's Method via SAS PROC MIANALYZE procedure for each endpoint.

APPENDIX 4. CRITERIA FOR POTENTIALLY CLINICALLY SIGNIFICANT AND CLINICALLY SIGNIFICANT ABNORMAL LABORATORY TESTS

Hemoglobin A1C criteria is explicitly stated in the table below.

All other criteria are met when both of the following occur:

- Post-baseline values meet the thresholds below
- Baseline values or any previous post-baseline values do not meet the thresholds below

Parameter	Unit	Lower Boundary	Upper Boundary
Hematology			
Hematocrit	%	≤0.8 × LLN	N/A
Hemoglobin	g/dL	≤10 g/dL	N/A
Platelet Count	10^9/ L	≤75*	≥700*
White Blood Cell Count	10^9/L	≤2.8	≥16
Serum Chemistry			1
Alanine Aminotransferase (ALT/SGPT)	U/L	N/A	>1 and $\leq 3 \times ULN$
Alanine Aminotransferase (ALT/SGPT)	U/L	N/A	>3 and $\leq 5 \times ULN*$
Alanine Aminotransferase (ALT/SGPT)	U/L	N/A	$>$ 5 and \leq 10 × ULN*
Alanine Aminotransferase (ALT/SGPT)	U/L	N/A	>10 and <20 × ULN*
Alanine Aminotransferase (ALT/SGPT)	U/L	N/A	>20 × ULN*
Alkaline Phosphatase	U/L	N/A	>2 × ULN*

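### In the unimputed MAR repeated-measures analysis, keep Day 90 with zero contrast weight, and state one visit set for it

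*SAP*

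**What the plan says.** The second co-primary endpoint averages percentage change in LDL-C over visits after Day 90 and up to Day 540. Its primary analysis (SAP 6.4.6.1) is an MMRM fitted to each of 100 datasets completed by the control-based pattern-mixture model, with the instruction "Note that Day 90 will be excluded from the MMRM". Appendix 1 repeats this: "Note that for time adjusted percentage change analyses (second co-primary efficacy endpoint) Day 90 will be excluded from the models".

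Section 6.4.6.1.1 adds an MMRM without imputation, assuming MAR, for each co-primary endpoint. The Day 510 entry states: "This will be the same model that is used as a sensitivity analysis for the second co-primary endpoint". The time-adjusted entry says the same in reverse. The same section describes the control-based sensitivity analysis at Day 510 as "using the same imputed datasets and MMRM model that was used for the second co-primary efficacy endpoint primary analysis".

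Appendix 1 opens by including the sensitivity MMRM for the first co-primary endpoint in its scope, and then gives the visits: "The visits will include Days 90, 150, 270, 330, 450, and 510, with Day 510 as the primary time-point". Day 540 is not in that list.

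**The concern.** There are two separate problems, both in the unimputed MAR analysis.

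The first is statistical. An endpoint that averages visits after Day 90 needs weight zero on Day 90 in the contrast. It does not need Day 90 removed as an outcome. Under the schedule of assessments, Day 90 is the first lipid measurement after baseline. A likelihood-based MMRM uses early outcomes, through the covariance matrix, to inform later missing ones, and this is what makes MAR plausible when dropout depends on early response. Without Day 90, a subject who leaves before the Day 150 window contributes nothing. The plan can produce such subjects: someone who declines further visits has an early end-of-study visit, and Table 2 of the SAP assigns any value from Day 61 to Day 120 to Day 90. Section 6.3.4.1 says retrieved data are used in all analyses, which would not be so for a value in that window.

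The second is specification. Under Appendix 1 the Day 510 model contains Day 90 and the time-adjusted model does not. Under section 6.4.6.1.1 they are one model. A programmer cannot follow both.

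At stake is a robustness analysis that protects less against early dropout than it could, and a choice of visit set left to whoever writes the code.

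**Working it through.** **The plan's own figures.** The documents give no figure for the Day 90 rule. The related figures reproduce. For dropout, 400 × 0.95 = 380 evaluable. For power with 190 per arm, difference 30 and SD 20, the standard error is 20 × √(2/190) = 2.05 and 30/2.05 = 14.6, far above 1.96. Power therefore exceeds 99.9%, consistent with the stated figure of more than 90%.

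**Primary analysis of the second co-primary endpoint.** Appendix 3 lists "Observed value of efficacy measurement at Day 90 (continuous") among the imputation variables and says of the monotone step: "After this step, the 100 datasets will be fully imputed". A subject with only a Day 90 value therefore stays in the ITT analysis, with later visits imputed. On complete data with an unstructured covariance and treatment-by-visit means, Day 90 can affect the later contrast only through the single baseline slope, since the sample code has no baseline-by-visit term. In 200 simulated complete datasets the treatment difference moved by 0.004 points on average and 0.040 at most. The standard error was 1.481 either way.

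**Subjects lost in the unimputed analysis.** Assume the planned 5% dropout is spread evenly over 540 days. The share leaving in the 60 days between Day 90 and Day 150 is 0.05 × 60/540 = 0.56%, and 0.0056 × 482 = 2.7, or about 3 subjects over both arms.

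**Effect on the estimate.** The same model was fitted with Day 90 (zero weight) and without it. Assumptions that are not in the documents: SD 20 percentage points at each visit, between-visit correlation 0.6, baseline SD 45 mg/dL, baseline slope −0.05, a true effect of −50 points at every visit, Day 540 included, equal weights, and maximum likelihood. Dropout occurs only in the inclisiran arm (241 of 482), right after Day 90. It is either random or has probability proportional to exp(z), where z is the standardised Day 90 outcome, so poor responders leave more often. There were 200 runs per row. Shift is the estimate without Day 90 minus the estimate with it; negative values favour inclisiran.

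| Share of arm leaving | Subjects with / without Day 90 | Shift, random | Shift, poor responders |
|---|---|---|---|
| 1% | 482 / 480 | 0.001 | −0.091 |
| 2.5% | 482 / 476 | −0.004 | −0.297 |
| 5% | 482 / 470 | −0.009 | −0.596 |

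Hand check: exp(z) weighting raises the dropouts' mean z by about 1, so at later visits they would be about 0.6 × 20 = 12 points worse. Removing a fraction f shifts the remaining mean by about 12f/(1 − f). For 2, 6 and 12 of 241 subjects this gives 0.10, 0.31 and 0.63, in line with the last column.

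**Against the test.** The standard error is about 1.5, so the largest shift is 0.596/1.496 = 0.4 standard errors. The assumed effect is 50/1.5, about 33 standard errors. The 30% reduction used for planning would be 30/1.5 = 20.

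**The passages side by side.** Sections 6.4.6.1 and 6.4.6.1.1 agree with each other if the Day 510 sensitivity models also omit Day 90. Appendix 1 rules that reading out: it ties the visit list containing Day 90 to Day 510 and limits the exclusion to the time-adjusted analyses.

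**The case against.** The best defence is that the exclusion is deliberate and harmless where it counts. The SAP explains that the endpoint describes steady state and that the Day 90 dose starts the six-monthly regimen, so fitting only later visits is coherent. Neither confirmatory test depends on the unimputed model: the first co-primary endpoint uses ANCOVA on washout-imputed data, and the second uses the imputed MMRM. Both endpoints have tipping-point analyses, and sites must follow subjects to Day 540 whatever their treatment status. All of this stands, and it is why the point is minor.

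A reader might infer from the sentence in section 6.4.6.1 that the plan discards early dropouts' data in the confirmatory analysis. The documents do not support that, because Day 90 enters through the imputation. Nor do they support changing every MMRM: on completed data nothing is gained, and the addendum shows that the SAP was final, the database locked and the study unblinded.

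It can also be said that the Appendix 1 visit list is generic and serves secondary endpoints too. But the appendix names the first co-primary sensitivity analysis as within its scope, so the conflict remains. Protocol section 10.4.3.1 also isolates the period after Day 90 through linear combinations of estimated means and mentions no removal of Day 90. SAP section 8 attributes changes to the primary analyses to FDA feedback without naming this one.

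**Conclusion.** The point holds for the unimputed MAR MMRM only. Excluding Day 90 there drops subjects with no later value and removes information on their missing visits. The SAP also contradicts itself on whether the Day 510 version contains Day 90.

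The size is small: about 3 of 482 subjects if 5% dropout is even over time. Under the simulation's assumptions the estimate moves by less than 0.01 points with random dropout. It moves by 0.09 to 0.60 points, in the direction that flatters inclisiran, if 1% to 5% of that arm leaves right after Day 90 with poor responders more likely to go. The even-dropout count lies near the low end of that range. No conclusion would change at the planned effect. The primary analysis of the second co-primary endpoint is essentially unaffected. This is a worthwhile clarification, not a threat to the result.

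**What to change.** - In the unimputed MAR MMRM, keep Day 90 as an outcome visit for both co-primary endpoints. Use the Day 510 contrast for the first and a linear combination with zero weight on Day 90 for the second. The two entries in section 6.4.6.1.1 are then one model, as they claim.
- Limit the Day 90 exclusion note in Appendix 1 to the imputed analysis, and leave that primary model as it is.
- State the visit set once in Appendix 1 and cross-refer to it from sections 6.4.6.1, 6.4.6.1.1 and 6.4.6.2. Add Day 540, since the endpoint runs to that visit and Appendix 3 imputes it. Say which set applies to the imputed Day 510 sensitivity analysis and to the time-adjusted absolute change; the current note names percentage change only.
- Give the correct reason: a zero-weight visit does not enter the contrast, but it does inform missing later values through the covariance. It would be wrong to say that it does not enter the estimate.

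The cost is wording and one model run. Because the study is unblinded, the sponsor should record which visit set was used and label any refit as supplementary.
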